## 19.4 Appendix A4 – CCE Image Reading Instructions

### Step 1: Clinical Site Sends CCE Raw Data to the Sponsor

Following the completion of the CCE procedure, the raw data and RAPID® video will be downloaded from the DR3 to the Given® workstation. A copy of the RAPID® raw data and video should be sent within **3 working days** to the sponsor who will forward it to the central reader for evaluation.

### Step 2: Sponsor Sends CCE Raw Data to the Central Reader

The sponsor should send the following information to the randomly assigned reader for each video with **2 working days** of receipt from the site:

- RAPID video
- Procedure date
- Subject code (initials and number)

### Step 3: Image Reading by Local and Central Readers

For each RAPID® video, the central reader will evaluate the following:

1. Adequacy of colon preparation for each colorectal segment (cecum, ascending, transverse, descending/sigmoid, and rectum) and for the overall colon using a validated system, as shown in Appendix A5. This information should be recorded in the CRF.
2. For CCE-detected polyps, tumors or lesions, the following information shall be documented as a video thumbnail (selected image within the video) and recorded in the CRF.
  - Location (cecum, ascending, transverse, descending/sigmoid, and rectum)
  - RAPID® time
  - Polyp size in millimeters. Size must be measured using the Polyp Size Estimation SW utility that will be provided as part of the RAPID® software.

Location in the colon will be estimated using visible landmarks, particularly the cecal landmarks and the anus, and the RAPID program, which displays the approximate position of the capsule in the abdominal-pelvic cavity. Capsule time to reach the cecum, the hepatic and splenic flexures, and time to exit the rectum will also be measured by the software.

Readers will trace the longest visible dimension of the polyp using a function within the software, which will automatically calculate the length. Readers will save all findings as photographs and detailed descriptions, and deliver to the sponsor within 2 weeks of reading.

All CCE local and central reading will be conducted in accordance with the sponsor's RAPID®8.3 software and RAPID® videos evaluation training.

Colonoscopy must not be performed by the same person who conducts the local reading.

### Step 4: Reader Sends CCE Results to the Sponsor

All findings will be saved as thumbnails, with detailed description of each finding, to create a detailed GRML file. Central readers will provide a report of their findings to the sponsor within 2 weeks of capsule ingestion in order to allow subjects to return within 5 weeks capsule ingestion procedure to

undergo confirmatory OC. The central readers will be required to return the following items to the sponsor:

- Signed RAPID® report
- GRML file
- Case Report Form (CRF)

*Step 5: Sponsor Sends CCE Results back to the Site*

Upon receipt, the sponsor will send the signed RAPID report, the signed cleansing evaluation form, and the case report form to a designated person at the relevant site. Local reader results will be read within 2 weeks and kept at the subject binder until confirmatory OC. The results will not be disclosed to the physician performing the colonoscopy until after the blinded colonoscopy is complete.

The GRML file will be provided to the relevant site upon specific request.

**19.5 Appendix A5 – CCE Bowel Cleansing Scale****Cleansing Level Scale for Colon Capsule Endoscopy**

Rating	Description
Poor	Inadequate
	Large amount of fecal residue precludes a complete examination
Fair	Inadequate, but examination completed
	Enough feces or turbid fluid to prevent a reliable examination
Good	Adequate
	Small amount of feces or turbid fluid not interfering with examination
Excellent	Adequate
	No more than small bits of adherent feces

Adapted from Leighton JA et al. Endoscopy 2011;43:123-7.

## **20.0 Appendix B – CTC Procedure Instructions**

The purpose of this multicenter, prospective, randomized study is to compare the diagnostic yield, accuracy, and safety of colon capsule endoscopy (CCE) and computed tomographic colonography (CTC) in the identification of colonic polyps in a screening population.

This appendix includes instructions for the CTC randomized procedure in 4 parts:

- Appendix B1 – CTC Bowel Preparation
- Appendix B2 – CTC Subject Instructions Form
- Appendix B3 – CTC Procedure Instructions
- Appendix B4 – CTC Image Reading Instructions
- Appendix B5 – CTC Bowel Cleansing, Distension, and Tagging Scale

**20.1 Appendix B1 – CTC Bowel Preparation**

Bowel preparation for CTC will follow the regimen below and includes stool tagging, laxative purgation, and fluid tagging.

**Magnesium Citrate Colon Preparation Procedure for Subjects Randomized to the CTC Arm**

Three Days Prior to the Procedure Day	Instructions
All Day	Low-residue diet
Two Days Prior to the Procedure Day	
All Day	Low-residue diet
The Day Before Procedure Day	
Meals	Clear liquid diet all day
Before 11am	Two 5 mg bisacodyl tablets plus 8 ounces of clear liquid
2pm	One bottle (296 ml) magnesium citrate followed by 6 cups of clear liquids
5pm	225 mL liquid barium sulfate suspension One bottle (296 ml) magnesium citrate followed by 6 cups of clear liquids
8pm	50 mL bottle of Omnipaque (iohexol) 350 mgI/mL mixed in 8 oz. clear liquid
Midnight	No food or water
Procedure Day	
Meals	None until after procedure

Adapted from: UW Health. Health Facts for You: Getting Ready for Your Virtual Colonoscopy (Routine VC Prep) [cited 2015 August 11]. Available from: <http://www.uwhealth.org/healthfacts/diagnostic-tests/7560.html>

**20.2 Appendix B2 – CTC Subject Instructions Form**

Subjects randomized to the CTC arm will be provided with a subject instructions form that details the bowel preparation procedure described above. This form will be used to document the subject's adherence to the procedure steps and will also serve as source data for CRF entries.

See attached document, "TOPAZ CTC Subject Instructions"

### 20.3 Appendix B3 – CTC Procedure Instructions

The subjects last bowel movement should be clear prior to beginning the CTC exam.

The CTC procedure and study interpretation will be conducted in accordance with the ACR–SAR–SCBT-MR Practice Parameter for the Performance of CT Colonography in Adults (Available from: <http://www.acr.org/quality-safety/standards-guidelines/practice-guidelines-by-modality/ct>) and other published literature (Johnson et al. N Engl J Med 2008;359:1207-17).

CTC examinations will occur at designated facilities with expertise in CTC procedures. ACR-SAR-SCBT-MR Practice Parameter certification is required prior to reading CTC study cases.

For CTC, colon insufflation will be performed with the subject in the lateral decubitus or supine position after placement of a catheter tip (with a retention balloon) in the rectum using an automated CO2 insufflator. The colon will be insufflated to a set pressure, which will likely require at least 2 liters of CO2.

The catheter will be left in the rectum, and, with the subject in the supine position, a CT scout image will be taken to confirm adequate colon distention. If adequate bowel distention is not achieved, additional air will be insufflated into the colon.

After scanning the subject in the supine position, the subject will be placed in the prone position, and additional CO2 will be administered. Subsequently, CT will be performed with the subject in the prone position. If a prone position is not possible for the subject, a right lateral decubitus position is preferred for optimal gas and fluid redistribution.

A low-dose technique without IV contrast administration or glucagon will be utilized.

Specific CT parameters include:

- 16 slice or greater MDCT
- Collimation: 0.5–1.0 mm
- Reconstructed slice thicknesses: 1–1.25 mm
- Reconstruction interval: 0.8 mm
- Pitch: 0.98–1.5
- Matrix: 512 × 512
- Field-of-view: to fit the subject
- 50 effective mAs
- Peak voltage: 120 kV
- Each series should be obtained in end expiration to minimize pressure effects of inflated lungs on the transverse colon

\*In case different CT machines are used, manufacture recommended protocol should be followed.

## 20.4 Appendix B4 – CTC Image Reading Instructions

### Step 1: CTC Site Conducts CTC Exam

### Step 2: CTC Radiologist Sends CTC Raw Data to the Sponsor

The site conducting the CTC should transfer the CTC DICOM file to the sponsor **within 3 working days** of the CTC exam.

### Step 3: Sponsor Sends the CTC Raw Data Files to the Central Reader

Central readers will be experienced, independent physicians trained to read CTC who are not site investigators. For each case, the reader should receive the following information **within 2 working days** of receipt from the CTC site:

- CTC DICOM file
- Procedure date
- Subject code (initials and number).

### Step 4: CTC Exam Reading

All CTC studies will first be read by local readers (radiologists) at the site conducting the CTC exam using their standard software. Workstations utilized for CTC interpretation should be able to display 2D and 3D data as well as prone and supine data side-by-side for interactive interrogation. The software should also allow the interpreting physician to change the window width and level settings interactively and in real time. Extracolonic structures will be documented at the time of the review of the colon.

For each CTC exam, local and central readers will evaluate the following:

1. Adequacy of colon preparation, distention, and fecal tagging for each colorectal segment (cecum, ascending, transverse, descending/sigmoid, and rectum) and for the overall colon using a validated system, as shown in Appendix B5. This information should be recorded in the CRF.
2. For detected polyps, tumors or lesions, the following information shall be documented as representative image (selected image within the file) and recorded in the CRF.
  - Location (cecum, ascending, transverse, descending/sigmoid, and rectum)
  - Distance in cm from the anus
  - Polyp size in millimeters.

### Step 5: Reader Sends CTC Results to the Sponsor

Analysis of CTC data by the central readers is to be performed using 3D software. The central readers will be required to read the CTC images in a timely manner (within 2 weeks) and send back to the sponsor the following items:

- Signed CTC report
- DICOM file
- Case Report Form (CRF)

### Step 6: Sponsor Sends CTC Results back to the Site

Upon receipt, the sponsor will send the signed CTC report and the case report form to a designated person at the relevant site. Local reader results will be read within 2 weeks and kept at the subject binder until

CONFIDENTIAL

**Medtronic**

confirmatory OC. The results will not be disclosed to the physician performing the colonoscopy until after the blinded colonoscopy is complete.

## 20.5 Appendix B5 – CTC Bowel Cleansing, Distension, and Tagging Scale

Quality of bowel preparation for CTC will be evaluated on the basis of colon cleanliness, distension, and fecal tagging in accordance with prior publications (Fletcher, AJR Am J Roentgenol 2013; 201:787–794).

The colon will be divided into five segments: cecum, ascending, transverse, descending/sigmoid, and rectum. For all evaluations, the worst section of a segment will be used to define the segmental score. Per segment scores will be averaged for overall scores of distention, fluid, and stool (quantity and size) scores. If one of the overall distention, fluid, or stool scores is considered inadequate, then the exam prep will be considered inadequate.

### Residual Fluid and Stool Grading

Rating		Description
0	Adequate	0% of the lumen filled with residual fluid or stool
1		<33% of the lumen filled with residual fluid or stool
2	Inadequate	33% of the lumen filled with residual fluid or stool both prone and supine
3		>33% of the lumen filled with residual fluid or stool both prone and supine

Adapted from Fletcher, AJR Am J Roentgenol 2013, 201:787–794

### Stool Size Grading

Rating		Description
0	Adequate	No stool
1		Stool $\leq$ 5 mm (could miss polyps < 5mm)
2	Inadequate	Stool 6–9 mm (could miss polyps 5-9 mm)
3		Stool $\geq$ 10 mm (could miss polyps $\geq$ 10mm)

Adapted from Fletcher, AJR Am J Roentgenol 2013; 201:787–794

### Segmental Distention Grading

Rating		Description
0	Adequate	>90% of estimated maximal distention
1		75–90% of estimated maximal distention
2	Inadequate	50–74% of estimated maximal distention
3		<50% of maximal distention

Adapted from Fletcher, AJR Am J Roentgenol 2013; 201:787–794

**21.0 Appendix C – Optical Colonoscopy (OC) Procedure Instructions**

The purpose of this multicenter, prospective, randomized study is to compare the diagnostic yield, accuracy, and safety of colon capsule endoscopy (CCE) and computed tomographic colonography (CTC) in the identification of colonic polyps in a screening population.

All subjects will undergo a confirmatory optical colonoscopy (OC) procedure within 5 weeks of the CCE ingestion or CTC procedure. The confirmatory OC will first be conducted blinded to the CCE/CTC results and then unblinded, if discrepancies in polyp detection are observed, as shown below.

Diagnostic yield of CCE/CTC will be calculated in relation to the confirmatory OC results.

This appendix includes instructions for the OC randomized procedure in 4 parts:

- Appendix C1 – OC Bowel Preparation
- Appendix C2 – OC Subject Instructions Form
- Appendix C3 – OC Procedure Instructions
- Appendix C4 – OC Bowel Cleansing Scale

### 21.1 Appendix C1 – OC Bowel Preparation

The OC bowel preparation is a standard bowel prep utilized in current medical practice and will include administration of Senna tablets, a clear liquid diet and administration of a purgative sulfate-free polyethylene glycol electrolyte lavage (SF-ELS) solution (e.g., NuLYTELY) divided into two doses: the first dose on the evening before the exam and the 2nd dose on the morning of the exam day (the 2nd dose may be consumed at the clinic or home, per physician discretion).

#### Colon Preparation Procedure for Optical Colonoscopy

Two Days Prior to the Procedure Day	Instructions
All Day	Drink at least 10 glasses of liquid
Bedtime	Four Senna tablets
The Day Before the Procedure Day	
Meals	Clear liquid diet all day
7:00pm – 9:00pm	2 liters sulfate-free PEG electrolyte lavage solution (such as ELS; NuLYTELY, Braintree Laboratories, Braintree, MA), one 8-10 oz. cup every 10-15 minutes.
Procedure Day	
12am to completion of optical colonoscopy procedure	None until after procedure
7am to approx. 8:30am	2 liters sulfate-free PEG electrolyte lavage solution (such as ELS; NuLYTELY, Braintree Laboratories, Braintree, MA), one 8-10 oz. cup every 10-15 minutes.
Per physician discretion	Conduct optical colonoscopy

CONFIDENTIAL

**Medtronic**

### **21.2 Appendix C2 – OC Subject Instructions Form**

During the OC bowel preparation procedure, subjects will be asked to use a Subject Instructions Form to document their activities. This form will be used to document the subject's adherence to the procedure steps. The Subject Instructions Form will also serve as source data for CRF entries.

See attached document, "TOPAZ OC Subject Instructions"

### 21.3 Appendix C3 – OC Procedure Instructions

The confirmatory OC will first be conducted blinded to the CCE/CTC results and then unblinded, if discrepancies in polyp detection are observed, as shown below. For the blinded OC procedure, the colonoscopist will be kept blinded to the CCE or CTC results until the OC procedure visualizes the entire colon. After the blinded colonoscopy, the colonoscopist will review the RAPID or CTC report with the CCE or CTC results. If results are not congruent, a second colonoscopy will be performed.

For both the blinded and unblinded OC studies:

- Study GI endoscopists (not the same GI physician that performs the local reading) will be trained by the sponsor on polyp size estimation using study designated biopsy forceps (Radial Jaw 4, by Boston Scientific), to confirm homogeneous methods between all participating study centers.
- The OC examination will be recorded electronically and sent to the sponsor. Only the subject study ID and initials should appear in the recorded video either by inserting the initials to the recording machine or by including a snapshot of the subject's initials written on a piece of paper at the beginning of the procedure. The withdrawal time will need to be at least 6 minutes as per common practice.
- Size measurement for every polyp using the reference forceps will be documented in a picture (i.e., open study forceps will be placed as close as possible to the polyp, on maximum linear dimension, while it is being photographed).
- All OC still pictures will be saved in a digital format (.tif or .bmp). Quality copies of the pictures taken during OC will be provided to the study sponsor with the OC report.
- These videos and pictures will be archived by the sponsor and may be used in future analyses to, for example, provide further information about observed lesions, to assess study quality, or add further information regarding comparisons between colonoscopy and capsule findings.

For each OC procedure the following information will be collected:

- Adequacy of colon preparation for each colorectal segment (cecum, ascending, transverse, descending/sigmoid, and rectum) and for the overall colon using a validated system, as shown in Appendix C4. This information should be recorded in the CRF.
- Colonoscopy report
- The following information will be collected and documented for each polyp detected:
  - Location: Colon segment (i.e., cecum, ascending, transverse, descending/sigmoid, and rectum)
  - Polyp size: Size must be measured by reference using the designated biopsy forceps (Radial Jaw 4, Boston Scientific)
  - Histology Report High Definition still pictures of the polyp with the reference forceps at the location
  - For unblinding procedure - Findings Confirmation Case Report Form

Note: Findings from the initial blinded OC will be documented separately from the unblinded OC on separate CRFs.

**21.4 Appendix C4 – OC Bowel Cleansing Scale**

**Cleansing Level Scale for Optical Colonoscopy**

Rating	Description
Poor	Inadequate
	Large amount of fecal residue precludes a complete examination
Fair	Inadequate, but examination completed
	Enough feces or turbid fluid to prevent a reliable examination
Good	Adequate
	Small amount of feces or turbid fluid not interfering with examination
Excellent	Adequate
	No more than small bits of adherent feces

Adapted from Leighton JA et al. Endoscopy 2011;43:123-7.

## **22.0 Appendix D – Patient Procedure Preference Sample Questionnaires**

The purpose of this multicenter, prospective, randomized study is to compare the diagnostic yield, accuracy, and safety of colon capsule endoscopy (CCE) and computed tomographic colonography (CTC) in the identification of colonic polyps in a screening population.

This appendix includes patient procedure preference sample questionnaires that may be used in the study. Data for patient procedure preference will be collected over the phone 5-9 days after the OC procedure.

- Appendix D1 – CTC versus OC Procedure Preference Sample Questionnaire
- Appendix D2 – CCE versus OC Procedure Preference Sample Questionnaire

22.1 Appendix D1 – CTC versus OC Procedure Preference Sample Questionnaire

Was subject follow-up performed?	 No  Yes
If Yes, date of follow-up	(dd-MMM-yyyy)
Which procedure would you prefer to have in the future?	 CTC Procedure  Optical Colonoscopy
Why do you prefer this procedure? (choose 2-3 that apply)	
 No time off work required if completed outside of a clinical trial	
 No need for someone to drive me	
 Prefer to be sedated for tube insertion	
 No need to be put to sleep	
 No need for an IV	
 Less bowel prep required	
 Less invasive	
 Less discomfort (specify):	
 Air pushed into colon was uncomfortable	
 Other	
 Less embarrassing	
 Exam took less time	
 More familiar with it	
 No need to drink chalky solution	
 Can collect tissue (biopsy) at same time	
 No radiation	
 Finds more polyps	
 Safer	
 Standard screening procedure	
 Cutting edge technology	
Comment	

22.2 Appendix D2 – CCE versus OC Procedure Preference Sample Questionnaire

Was subject follow-up performed?		 No  Yes
If Yes, date of follow-up		(dd-MMM-yyyy)
Which procedure would you prefer to have in the future?	 CCE Procedure  Optical Colonoscopy	
Why do you prefer this procedure? (choose 2-3 that apply)		
 No time off work required if completed outside of a clinical trial		
 No need for someone to drive me		
 No need to be put to sleep		
 No need for an IV		
 Less bowel prep required		
 Can move around during procedure		
 Less invasive		
 Less embarrassing		
 Exam took less time		
 More familiar with it		
 No need to drink chalky solution		
 Can collect tissue (biopsy) at same time		
 Finds more polyps		
 Safer		
 Standard screening procedure		
 Cutting edge technology		
Comment		

### 23.0 Appendix E – Matching Algorithm

To address inherent uncertainties in the comparison of polyp localizations and sizes, a polyp-matching algorithm will be used to determine the agreement between CCE/CTC and OC. The first step of this procedure is to identify all polyps  $\geq 6$ mm detected by any method (OC, CCE, or CTC). The polyp with the largest estimated diameter of either OC or CCE/CTC will be referred to as the ‘reference’ polyp. The colon segment location (cecum, ascending, transverse, descending/sigmoid, or rectum) of the reference polyp will be determined and recorded. The largest polyp identified using the other method within the same or an immediately adjacent segment location of the “reference” polyp will be used to determine agreement based on a size matching algorithm. If there were two polyps of equal size that were “the largest” and located in different segments of the colon, then the location and size matching algorithm will be repeated for each of these reference polyps to determine agreement of CCE/CTC with OC.

For a given polyp to be considered a match between CCE/CTC and OC, it has to be assessed within 50% (plus or minus) of the size of the largest estimate of the two studies (CCE and OC or CTC and OC) and must appear within the same or immediately adjacent colon segments.

For example, if CCE detected a 10 mm polyp, the  $\pm 50\%$  range would be 5-15 mm. If colonoscopy detected a 6 mm polyp ( $\pm 50\%$  range = 3-9mm) in the same or immediately adjacent segment, the 2 polyps would be considered a match (CCE true positive) because the two ranges overlap.

The “reference” polyp size will then be used to assign the polyp to the following groups:  $\geq 6$  mm, and/or  $\geq 10$  mm in size. For each subject, the CCE/CTC evaluation will be classified into one of four categories of agreement relative to OC, as shown in Table 3.

Table 3. Polyp Matching Accuracy Assessment

Findings of CCE or CTC	Findings of blinded or unblinded colonoscopy	
	Positive	Negative
Positive	
True positive (A)
 
Polyps <math>\geq 6</math>mm: Polyp matching exists and “reference” polyp size is <math>\geq 6</math> mm
 
Polyps <math>\geq 10</math>mm: Polyp matching exists and “reference” polyp size is <math>\geq 10</math> mm
	
False positive (B)
 
Polyps <math>\geq 6</math>mm: No polyp matching and CCE/CTC is <math>\geq 6</math> mm
 
Polyps <math>\geq 10</math>mm: No polyp matching and CCE/CTC polyp is <math>\geq 10</math> mm

Negative	
False negative (C)
 
Polyps <math>\geq 6</math>mm: No polyp matching and OC polyp is <math>\geq 6</math> mm
 
Polyps <math>\geq 10</math>mm: No polyp matching and OC polyp is <math>\geq 10</math> mm
	
True negative (D)
 
Polyps <math>\geq 6</math>mm: All reported polyps are <math>< 6</math> mm
 
Polyps <math>\geq 10</math>mm: All reported polyps are <math>< 6</math> mm, or Polyp matching exists and “reference” polyp size is <math>< 10</math> mm

The accuracy measures will be calculated based on the matched results, including sensitivity, specificity, positive predictive value (PPV) and negative predictive value (NPV).

Additionally, sensitivity analyses including varying matching sizes and using OC as the reference will be performed to assess the robustness of the results.

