**8.2 Primary Effectiveness Endpoint**

The primary effectiveness endpoint is the diagnostic yield (proportion of subjects shown to have an actionable lesion, defined as any polyp or mass lesion  $\geq 6$  mm) by capsule colon endoscopy as compared to computed tomographic colonography. Diagnostic yield of CCE and CTC will be calculated in relation to the confirmatory OC results.

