#### 8.11.1 OC Procedure

All subjects will undergo a confirmatory OC procedure within 5 weeks of the randomized CCE or CTC procedure. The confirmatory OC will be conducted once or twice, depending on findings compared to CCE or CTC, if discrepancies between results exist. For the first (blinded) OC procedure, the operator must be blinded to both the central reader results and any local reader reports of the randomized CCE/CTC results. After the blinded OC procedure, the operator will read the central reader results for CCE/CTC. If CCE/CTC results are not congruent to the blinded OC procedure results, an unblinded OC procedure will be performed to verify polyp presence. Instructions for the bowel preparation and conduct of the OC procedure are provided in Appendix C.

Diagnostic yield of CCE/CTC will be calculated in relation to the confirmatory OC results. See Appendix D for details on polyp-matching algorithm.

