### 9.3 Effectiveness Analyses

All effectiveness variables will be summarized using descriptive statistics. The difference between treatment groups in categorical variables will be tested using two-sided Chi-square test or Fisher's exact test as appropriate. The difference between treatment groups in continuous variables will be tested using two-sided t-test or non-parametric Wilcoxon rank sum test as appropriate.

- Sensitivity, specificity, NPV, and PPV for the detection of polyps  $\geq 6$  mm and  $\geq 10$  mm (per subject) relative to the confirmatory OC exam
- [REDACTED]
- [REDACTED]
- [REDACTED]
- [REDACTED]
- [REDACTED]
- [REDACTED]
- [REDACTED]

- [REDACTED]
- [REDACTED]

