#### 9.6 Interim Analyses

Interim analyses are planned after each 80 subjects (40 per arm) have completed the primary endpoint, until 320 total subjects or the non-inferiority for the primary endpoint is met (whichever occurs first).

Additionally, sample size re-assessments will be carried out during interim analyses. The conditional power will be calculated to determine if a sample size adjustment is necessary. There will not be necessary to adjust the alpha level if the conditional power is greater than 50% (i.e., within the promising zone). If the chance of success is too low (i.e. <10%), *early stopping for futility may be considered*.

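### Appendix E does not give one class per subject: Table 3 overlaps and has a gap, the size tolerance is stated two ways, ties are unresolved, and its link to the primary yield needs reconciling

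*Combined protocol and SAP*

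**What the plan says.** Section 8.2 defines the primary yield as the "proportion of subjects shown to have an actionable lesion, defined as any polyp or mass lesion" of at least 6 mm, calculated in relation to OC. Section 8.11.1 repeats that yield is taken relative to OC and then says "See Appendix D for details on polyp-matching algorithm". Appendix D holds the preference questionnaires; the algorithm is in Appendix E.

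Appendix E first lists all polyps ≥6 mm seen by any method, then fixes the lesion to be judged: "The polyp with the largest estimated diameter of either OC or CCE/CTC will be referred to as the" reference polyp. It is compared with the largest lesion the other method found in the same or a neighbouring segment. If two equal-largest polyps lie in different segments, "then the location and size matching algorithm will be repeated for each of these reference polyps to determine agreement". Each subject's CCE/CTC evaluation is then "classified into one of four categories of agreement relative to OC", using Table 3.

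Section 9.3 uses the result at two cut-offs: "Sensitivity, specificity, NPV, and PPV for the detection of polyps" ≥6 mm and ≥10 mm. Appendix E also plans sensitivity analyses with other size tolerances and with OC as the reference.

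**The concern.** A classification rule must put every subject in exactly one class, so that two analysts with the same data obtain the same table. Appendix E does not do this at either cut-off, and it states its size tolerance in two ways that disagree.

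The stakes differ by part. The overlap and the gap in Table 3 do not alter the true positive count; they affect sensitivity, specificity, PPV and NPV. The tolerance, the tie rule and the choice between the largest lesion and any lesion can change who is a true positive. If yield is counted through Appendix E, as Section 8.11.1 implies, they can also change who is a primary success.

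**Working it through.** Inputs: the Appendix E rules, the four cells of Table 3, the definition in Section 8.2 and the cut-offs in Section 9.3. L is the larger reading and S the smaller, in mm.

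**1. Table 3 at ≥6 mm.** Take CCE/CTC 8 mm in the cecum and OC 7 mm in the rectum. The segments are not adjacent, so there is no match.
- False positive needs no match and CCE/CTC ≥6 mm: met (8).
- False negative needs no match and OC ≥6 mm: met (7).
- Read literally, the subject is in both cells.
- If the row and column headings are added as conditions, the subject is positive on both methods and belongs in the true positive quadrant. That cell requires a match, so the subject fits no cell.
- If the method holding the unmatched reference polyp decides, the 8 mm CCE/CTC reading makes this a false positive. Table 3 does not state this reading, and it fails when sizes are equal (8 mm cecum by CCE/CTC, 8 mm rectum by OC).

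Called false positive, the subject lowers specificity and PPV. Called false negative, the subject lowers sensitivity and NPV.

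**2. Table 3 at ≥10 mm.** Take CCE/CTC 8 mm and OC nothing.
- True positive: no match, not met.
- False positive: 8 < 10, not met.
- False negative: no OC polyp, not met.
- True negative needs all polyps <6 mm (8 is not) or a match with a reference <10 mm (there is none): not met.

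The subject is negative at 10 mm by both methods, yet is missing from TN in specificity = TN/(TN + FP) and NPV = TN/(TN + FN).

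**3. Size tolerance.** The plan's own example, 10 mm against 6 mm:
- Rule in words, within 50% of the larger: S ≥ L/2. Here 6 ≥ 5, a match.
- Reason given in the example, overlapping ±50% ranges: 0.5L ≤ 1.5S, so S ≥ L/3. The ranges are 5–15 and 3–9, a match.

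The example passes both and settles nothing. Now 15 mm against 6 mm in the same segment:
- In words: 6 < 7.5, no match.
- By overlap: 7.5–22.5 and 3–9 share 7.5–9, so a match and a true positive.

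The two differ whenever L/3 ≤ S < L/2.

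**4. Ties.** CCE/CTC 10 mm in the cecum and 10 mm in the rectum; OC 9 mm in the rectum. The cecal reference is unmatched and the rectal one is matched (9 ≥ 5). No rule combines the two results.

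**5. Largest against any.** Both methods find an 8 mm rectal lesion, and one method alone reports a 12 mm cecal lesion. Section 8.2 would count the subject, since a lesion ≥6 mm is found and confirmed. Appendix E takes the 12 mm lesion as reference, finds nothing near it by the other method, and does not give a true positive.

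**The case against.** Several counter-arguments have force.

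- **The overlap depends on the reading.** Letting the unmatched reference polyp decide removes most of it. This stands as a possible repair, but cells B and C do not mention the reference, and equal sizes remain.
- **The gap has an obvious repair.** It exists only at ≥10 mm, the secondary endpoints in Section 8.3 are at ≥6 mm, and true negative is the natural class. This also stands, but Section 9.3 uses ≥10 mm and the text must say so.
- **The tolerances rarely differ.** Among whole-mm pairs with both readings from 6 to 15 mm, they disagree for 4 of 55: 13 and 6, 14 and 6, 15 and 6, 15 and 7. A Clinical Events Committee adjudicates discrepant OC sizes, and other tolerances are planned as sensitivity analyses. Neither says which tolerance is primary.
- **Appendix E may not govern yield.** It names only the accuracy measures, and the link is one miscited sentence. But if it does not apply, the plan gives no rule for confirming a lesion against OC for the primary endpoint.
- **OC as reference is already planned.** This rescues case 5 when the extra 12 mm finding is by CCE/CTC, but not when OC holds it.

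A reader might infer that all-lesion matching must become primary. The documents do not support that. It would score a test that missed a 12 mm lesion as a true positive because it found an 8 mm one, and it gives more chances of a coincidental match.

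A reader might also infer that an 8 mm CCE/CTC reading paired with a 5 mm OC reading is wrongly a true positive. That is not settled. The opening step of Appendix E leaves unclear whether readings below 6 mm enter matching, and Section 8.11.1 says "an unblinded OC procedure will be performed to verify polyp presence", which concerns presence rather than size.

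**Conclusion.** The point holds as a defect of specification. As written, Appendix E does not assign exactly one class per subject, states its size tolerance in two incompatible ways, leaves discordant ties open, and has not been reconciled with Section 8.2.

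Its practical size cannot be stated, because the documents do not say how often these patterns occur. For scale only: Section 9.6 says "Interim analyses are planned after each 80 subjects (40 per arm) have completed the primary endpoint". One reclassified subject moves the yield difference by 1/40 = 2.5 points at the first look and by 1/160 = 0.6 points at the maximum size, against a 5-point margin. That is the weight of one subject, not an estimate of how many are affected.

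A reader might infer a biased CCE–CTC comparison. The documents do not show one. The same rules apply in both arms, and bias would need sizing error or large unmatched findings to differ by modality; no data on that are given. The case rests on the literal text of Appendix E and, for the primary endpoint, on taking Section 8.11.1 to mean that algorithm.

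**What to change.** 1. Rewrite Table 3 as an ordered rule at each cut-off. For example: true positive if a qualifying match exists; otherwise false negative if OC has a lesion at or above the cut-off; otherwise false positive if CCE/CTC has one; otherwise true negative. Unmatched findings below 10 mm then become true negatives at ≥10 mm. Report how many subjects meet both the false positive and false negative conditions.
2. Adopt one tolerance as primary and use the other among the planned size-tolerance analyses.
3. State how discordant ties are combined and whether readings below 6 mm can enter matching.
4. Correct Section 8.11.1 to cite Appendix E. State in Section 8.2 or 9.2 whether yield uses the largest-polyp rule or any matched lesion ≥6 mm, and report the other as a sensitivity analysis.

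Cost: wording and some programming. Size and segment are already recorded for each polyp under Appendices A4, B4 and C3, so no new data are needed. Reported yields or accuracy figures may shift slightly.
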